6. RATIONALE AND BACKGROUND

6.1. Background

Pregnant women are recognised as a group at increased risk of severe disease and death secondary to influenza infection mainly based on observations of excess influenza-related mortality in pregnant women during historical and recent pandemics [Harris, 1919; Freeman, 1959, Siston, 2010] and higher rates of influenza-related morbidity requiring hospitalisation during seasonal epidemics [Dodds, 2007; Neuzil, 1998; Mertz, 2013]. For example, in the United States, pregnant women had a 4-fold greater risk of hospitalisation due to A/H1N1 infections compared to the general population in the pandemic of 2009/2010 [Jamieson, 2009]. In addition, influenza and fever may increase the risk of adverse pregnancy outcomes [Meijer, 2015; Siston, 2010; Mosby, 2011; Haberg, 2013]. These effects were confirmed in the United Kingdom where risks of perinatal mortality, as well as preterm birth, were 4-fold greater in mothers infected with A/H1N1 during pregnancy [Pierce, 2011]. Furthermore, a recent systematic review and meta-analysis reported an association between severe A/H1N1 disease and preterm birth and foetal death [Fell, 2017].

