8.3.1. Exposure definitions

This pregnancy registry is strictly observational and confirmed exposure to IV zanamivir at any time during pregnancy is a condition of enrolment. The exposure of interest is exposure to at least one dose of IV zanamivir during pregnancy. If the anti-influenza medication to which the woman was exposed cannot be ascertained, an unknown exposure cohort will be established and analysed separately.

Data to be collected include the date of medication exposure and dose.

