8.3.2. Outcome definitions

There are three groups of outcomes of interest:

Maternal outcomes

• Maternal death during pregnancy and up to 42 days after delivery.

Pregnancy outcomes

- Live birth defined as an infant born alive.
- Spontaneous abortion (SAB) in clinically recognized pregnancies defined as foetal death or expulsion of products of conception prior to 20 weeks' gestation, or if gestational age is unknown, weighing less than 500g.
- Stillbirths defined as a foetal death occurring at 20 weeks' gestation or greater, or if gestational age is unknown, a foetus weighing 500 g or more.
- IAB defined as voluntary interruption of pregnancy, including pregnancy termination that occurs electively, to preserve maternal health, or due to foetal abnormalities.

Birth outcomes

- Prematurity defined as an infant born at gestational age <37 weeks.
- SGA defined as an infant born with a birth weight less than the 10th centile for the corresponding gestational age.
- LBW defined as an infant whose birth weight is <2500 g.
- Neonatal death defined as death of the infant within 28 days of birth.
- Major congenital malformation (MCM) defined according to EUROCAT criteria
- EUROCAT includes all major structural malformations and chromosomal malformations. Minor anomalies are excluded (as defined in Section 3.2 of the coding guide) and cases with more than one malformation type are only counted once for the calculation of overall malformation prevalence.

Maternal and infant follow up is proposed to 3 months after birth. Longer term follow-up is not proposed as there are no pre-clinical or clinical data to suggest a signal for developmental delay. Hence, it is impossible to determine an appropriate longer term follow up period which differs substantially according to the type of developmental adverse outcome of interest. As the majority of major malformations are detected at birth, a three month follow up period is deemed adequate to maximize capture of major malformations.

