8.3.3. Confounders and effect modifiers

Additional data will be collected as follows:

Maternal characteristics: Age, ethnicity, country.

Prenatal data: Last menstrual period (LMP), EDD, corrected estimated date of delivery (CEDD).

Prenatal tests: Name of test, date of test, result.

Obstetrical history: Previous pregnancies: live births, stillbirths, SABs, IABs, births with MCMs and family history of MCMs.

Pregnancy complications including preterm labour, pre-eclampsia and placental abruption.

Concurrent medical conditions influenza: including details of influenza episode such as length of hospital stay, HDU/ICU stay (and length of stay), supplemental oxygen, associated complications of influenza (including bacterial pneumonia, sepsis, myocarditis, encephalitis, acute respiratory distress, respiratory failure, bronchitis).

Concurrent medical conditions other: with emphasis on diabetes, hypertension, asthma and autoimmune conditions.

Concomitant medications and vaccines: Medications of specific interest will include teratogens based on the old FDA classification of medications labelled as category X. Lists of medications associated with teratogenicity will be taken from Briggs, 2009 which is consistent with the list used by the clinical geneticist of the North American Anti-Epileptic Drug Register [Holmes, 2004; Correa-Villasenor, 2003;. Medications will then be classified into strong teratogens (e.g., isotretinoin, thalidomide) and more modest teratogens (e.g., carbamazepine).

Tobacco use

Infant gender and multiple gestations

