8.4. Data sources

The current UKOSS/INOSS reporters will serve as data reporters identifying exposures for the registry within the UKOSS and INOSS networks. The registry is strictly observational; the schedule of health care visits and encounters as well as all treatment regimens will be determined by the treating HCP. There will be no additional laboratory tests or assessments required as part of this registry. Only data noted as part of routine care will be collected. Maternal characteristics and outcome data will be provided by research staff, where accessible. To aid follow up, the mother will be asked to consent to medical record release and further contact to facilitate pregnancy and infant follow up.

Additionally, the teratologist/geneticist on the scientific advisory committee (SAC) will provide an opinion regarding the possible temporal association of the IV zanamivir

exposure to the development of any observed congenital malformations. If additional information is needed to aid in classification or temporality assessment, the teratologist will request additional information using a targeted follow up process. The SAC will meet periodically to review the data including a discussion of the MCM cases and their classification and temporality with the teratologist and to reach a consensus on the coding and classification of MCMs and other primary endpoints. Healthcare providers may also report de-identified data to the registry. This could include exposures and outcomes identified through anonymised healthcare electronic medical record data sources.

A summary of data that will be collected at specific time points and the source of data are provided in Section 8.6.2.1.

For critical data points, if there are outstanding questions, discrepancies between forms, or missing data, the appropriate reporter will be contacted for clarification. Up to three subsequent attempts, as necessary, will be made at regular intervals (e.g. every two weeks).

Exposure operational definition

At least one dose of IV zanamivir administered at any time during pregnancy will constitute exposure. If the anti-influenza medication to which the woman was exposed cannot be ascertained, an unknown exposure cohort will be established and -analysed separately. Given the short half-life of IV zanamivir (two hours) the start of the exposure window will be conception estimated as described below.

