8.7.2. Exploratory analysis

Analyses will be stratified by trimester of exposure and other subgroups of interest, potentially including number of doses of IV zanamivir received, gestational age at enrolment and maternal age. Additional details on subgroup analyses will be described in the SAP. Comparisons may be made to external or internal cohorts, if appropriate.

Additional analyses may stratify by the variables listed below:

- Maternal characteristics (e.g., country)
- Previous pregnancy outcomes (e.g., MCMs, stillbirth)
- Pregnancy complications (e.g., preterm labour, pre-eclampsia, placental abruption)
- Influenza episode (e.g. length of hospital stay, ICU stay, oxygen requirements)
- Co-morbidities (e.g., diabetes, hypertension)
- Concomitant exposures (e.g., teratogenic medications, tobacco)
- Infant/foetus gender and multiple gestations.

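### Preterm births already under way before the first dose count as exposed outcomes, and complications used as confounders or strata carry no onset date

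*Protocol*

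**What the plan says.** Exposure is defined in section 8.4 as "At least one dose of IV zanamivir administered at any time during pregnancy will constitute exposure", with no condition on the state of the pregnancy at that dose. Section 8.3.1 adds: "Data to be collected include the date of medication exposure and dose". Section 8.3.2 defines prematurity by gestational age at birth alone, and section 8.7.1 divides preterm live births by all live births.

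Under section 8.7, a woman enrolled before the end of pregnancy is a traditional prospective report. Traditional and pure prospective reports together form the primary population.

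Timing relative to the drug is reviewed for malformations only: in section 8.4 the teratologist or geneticist gives an "opinion regarding the possible temporal association of the IV zanamivir" exposure to any malformation seen. For the other primary endpoints the committee's stated task is coding and classification.

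Section 8.3.3, headed as confounders and effect modifiers, lists "Pregnancy complications including preterm labour, pre-eclampsia and placental abruption". It gives no onset date for these, although the prenatal tests in the same list do carry a date. Section 8.7.2 offers the same items as optional strata: "Pregnancy complications (e.g., preterm labour, pre-eclampsia, placental abruption". The table in section 8.6.2.1 has complications recorded at registration and updated since the previous contact.

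**The concern.** The protocol's own background makes the sequence foreseeable. Section 6.1 cites a review that "reported an association between severe A/H1N1 disease and preterm birth and foetal death", and a fourfold preterm risk with maternal A/H1N1 infection. The product is indicated for complicated disease. A woman may therefore already be in preterm labour, or have had delivery decided, when she receives her first dose. If she is enrolled before delivery, her preterm birth enters the primary numerator as an exposed event, although the drug cannot have started it.

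The undated complications add a second problem. One that began before the dose is a baseline characteristic; one that began afterwards may be an effect of the drug. Without dates the two are mixed. Stratifying preterm birth by preterm labour would condition on the pathway to the outcome and could hide a real effect.

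The preterm estimate is one of the figures read for a safety signal, so it could be pushed up by the first problem, and its stratified versions pulled down by the second.

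**Working it through.** **1. Path into the primary numerator.** Take a woman in preterm labour who receives one dose, is enrolled the same day and delivers a live infant at 33 weeks.
- Exposed: yes (8.4).
- Prospective: yes, enrolled before the end of pregnancy (8.7).
- Primary population: yes (8.7, Analysis Population).
- Preterm: yes, below 37 weeks (8.3.2).
- Counted in numerator and denominator: yes (8.7.1).

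No step asks when labour began.

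**2. Can the order be recovered later?** The dose date is collected. Complications are recorded by contact, and registration itself follows exposure because confirmed exposure is a condition of enrolment (8.3.1). A complication noted at registration may thus have begun before or after the dose. On the variables listed, the order is not recoverable.

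**3. The protocol's own figure.** Inputs from section 8.5: reference p0 = 0.076, N = 100 live births, 1-sided 5%, power 80%, binomial.
- The smallest r with P(X ≥ r | 100, 0.076) ≤ 0.05 is r = 13: P(X ≥ 13) = 0.0398, whereas P(X ≥ 12) = 0.077.
- Solving P(X ≥ 13 | 100, p1) = 0.80 gives p1/p0 = 2.05, the entry in Table 1.
- For N = 150, r = 18 (0.0365) and the ratio is 1.85, again as in Table 1.

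**4. Effect of pre-dose events.** Let k live births be preterm deliveries under way before the dose, and let the other N − k follow 7.6% with no drug effect. The chance of reaching r is P(Bin(N − k, 0.076) ≥ r − k). The values of k are assumptions.

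| k | N = 100: P(X ≥ 13) | N = 150: P(X ≥ 18) |
|---|---|---|
| 0 | 4.0% | 3.6% |
| 3 | Bin(97) ≥ 10: 20% | Bin(147) ≥ 15: 15% |
| 5 | Bin(95) ≥ 8: 44% | Bin(145) ≥ 13: 31% |
| 8 | Bin(92) ≥ 5: 84% | Bin(142) ≥ 10: 64% |

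Expected prevalence at N = 100 and k = 5: (5 + 95 × 0.076)/100 = 12.2%, a ratio of 12.2/7.6 = 1.61 to the reference.

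**5. What this does not measure.** If influenza itself doubled preterm risk (15.2%), P(X ≥ 13 | 100, 0.152) = 77% with no drug effect; at the cited fourfold risk (30.4%) it exceeds 99.9%. That excess comes from using a general-population comparator. It is a separate matter, and ordering events against the dose would not remove it.

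**6. Foetal death.** Stillbirth is defined without reference to the dose: "Stillbirths defined as a foetal death occurring at 20 weeks' gestation or greater". But enrolment requires confirmed exposure, so a death diagnosed before the dose is also known before enrolment. Section 8.7 defines prospective registration as preceding knowledge of the outcome and names foetal loss among the ends of pregnancy. Such a report is retrospective and is initially analysed separately.

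**The case against.** The strongest replies are these.

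- **The registry is descriptive.** Correct: it sets no threshold of 13, so the percentages illustrate how the planned 1-sided comparison would behave and are not an operating rule. The model also adds the k events to a full 7.6% in all other births, ignoring overlap with background preterm birth, so it sits at the upper end. This limits the size and leaves the mechanism intact.
- **Complications are optional strata only.** Also correct. No adjustment model uses them, and the protocol does not say that preterm birth will be stratified by preterm labour. The list permits it without excluding it.
- **Onset dates are form-level or SAP detail.** Partly. Enrolment close to exposure and the recorded dose date give some ordering, and targeted follow-up can characterise losses. But section 8.3.3 lists what is collected, and an SAP cannot order events whose dates were never recorded.
- **Excluding pre-dose labour breaks comparability.** This stands. The 7.6% reference counts every preterm birth, so removing some from the exposed group alone can mask a signal. The restricted estimate therefore belongs as a sensitivity analysis.

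A reader might also infer that foetal deaths established before the dose inflate the primary stillbirth estimate. The documents do not support that, for the reason in step 6. What remains open is a death diagnosed but not yet delivered, if the end of pregnancy is read as delivery; de-identified network reports, which section 8.7 classes as prospective without an ordering test, although it also places them in secondary analyses; and any later pooling of retrospective reports.

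**Conclusion.** The point holds for preterm birth and for the undated complications. The protocol has no rule for preterm labour or a delivery decision that came before the first dose, and the variables it lists do not allow one to be applied afterwards. With 3 to 8 such births per 100, the chance of an apparent excess without any drug effect moves from 4.0% to between 20% and 84%; per 150 live births it moves from 3.6% to between 15% and 64%. These figures rest on assumed counts, on no overlap with background preterm birth, and on reading the 1-sided 5% comparison as a signal.

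It would go too far to conclude that the exposure definition charges the effects of influenza to the drug in general. Most of that confounding arises from the general-population comparator. Section 8.2 acknowledges this and says that disease severity will be considered to the extent possible.

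**What to change.** - **8.3.3 and the eCRF:** record the onset date of preterm labour or the date of the decision to deliver, the onset date of each listed complication, and the date of foetal-death diagnosis, all against the date and time of the first dose.
- **8.7.1:** keep the all-births preterm estimate as primary. Add a sensitivity estimate that removes from numerator and denominator pregnancies in preterm labour, or with delivery already decided, before the first dose. State beside it that the external reference counts all preterm births, so the restricted estimate may understate the comparison.
- **8.7.2:** use only complications with onset before the first dose as baseline strata, and report later ones as outcomes.
- **8.7, report classification:** state that a foetal death diagnosed before the first dose but not yet delivered is a retrospective report. Apply the same ordering to de-identified reports and to any pooling of retrospective reports.

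The cost is a few dates, to be taken from the medical record where they are noted, and one extra tabulation. Some onset dates will be approximate, the restricted estimate uses slightly fewer pregnancies, and it is less comparable with the general-population reference.

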IV zanamivir exposure will be further categorized by earliest trimester of exposure. For this registry, gestational weeks will be estimated from the most reliable EDD as reported by the HCP. If a CEDD is provided by the HCP, it will be used instead. The date of conception will be calculated as the most reliable EDD/CEDD minus 38 weeks. If the EDD is not available or never estimated, the first day of the LMP may be used to estimate gestational age. The second trimester will be considered to begin at week 14 after the date of conception or LMP, and the beginning of the third trimester, at week 28. If there is a discrepancy between gestational age calculated from LMP and reported gestational age, the HCP will be asked to verify the data.

If HCPs provide de-identified data to the registry, they must be able to verify the date of exposure to IV zanamivir. Such data may come from data collected both within and outside of the UKOSS/INOSS network. For example, UKOSS has ethical approval to collect a minimum exposure and outcome dataset on women exposed to new influenza treatments (including IV zanamivir) with a waiver of informed consent. This will enable capture of some data on women who may be exposed to IV zanamivir during hospitalisation with complicated influenza, but do not consent to participate in this study with more complete data collection. A similar situation may arise with other INOSS centres. Other potential de-identified data sources include anonymised healthcare data sources.

Outcome operational definition

All outcome variables will be provided by research staff at sites. They will be asked to describe any MCMs observed in the infant or foetus and will also be asked to report the

gestational age and birth weight. These two variables will be used to calculate preterm birth, LBW, and SGA. Data will be abstracted from medical records. As described above a teratologist/ geneticist will review all reported congenital anomalies and classify them using the EUROCAT system [EUROCAT, 2017].

Operational variable(s) definition

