The prevalence of preterm births, SGA and LBW will be calculated as proportions, with the number of live births as the denominator. Because MCMs are often associated with preterm birth and LBW, sensitivity analyses will be performed excluding infants with MCMs from the numerator and denominator when prevalence estimates are determined for these outcomes.

Formulas for the calculation of prevalence of the primary outcomes are presented below:

Preterm birth prevalence =	Number of preterm live births Number of live births
SGA prevalence =	Number of SGA live births Number of live births
LBW prevalence =	Number of LBW live births Number of live births
MCM prevalence =	Number of live births and foetal losses occurring at ≥ 20 weeks gestation with MCM Number of live births (all) plus number of foetal losses with MCM

Due to inconsistent ascertainment of malformations in early foetal losses these are not included in analyses. Furthermore, a conservative approach is taken to only include foetal losses ≥ 20 weeks with MCMs, rather than all foetal losses, in the denominator. This will result in an over-estimation of risk.

Because most structural defects have their origins in the first trimester of pregnancy during the period of organogenesis, analyses of MCMs will be stratified by trimester of exposure, if applicable. The second trimester will start at 14 weeks gestation and the third trimester will start at 28 weeks gestation. The prevalence of combined MCMs reported to the registry will be calculated as a proportion with the number of MCMs in live births and foetal losses as the numerator and the number of all live births plus foetal losses with a MCM as the denominator. Pregnancy losses with reported MCMs occurring at or after 20 weeks' gestation will be included in the numerator of the estimate of risk for MCMs to increase sensitivity. The prevalence of combined MCMs in exposed cases will be compared with that reported to EUROCAT AND MACDP. Only cases meeting the EUROCAT criteria will be included in the primary analysis.

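### Section 8.4 counts the trimester cut-points from conception or LMP, two origins 2 weeks apart; the default conception branch contradicts the gestational-age cut-points in 8.7.1

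*Protocol*

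**What the plan says.** The operational definition of exposure in Protocol section 8.4 makes trimester a classifying variable: "IV zanamivir exposure will be further categorized by earliest trimester of exposure". On dating, "gestational weeks will be estimated from the most reliable EDD as reported by the HCP", with the CEDD replacing the EDD where one is given. Then: "The date of conception will be calculated as the most reliable EDD/CEDD minus 38 weeks". LMP is the fallback: "If the EDD is not available or never estimated, the first day of the LMP may be used to estimate gestational age". The first cut-point follows: "The second trimester will be considered to begin at week 14 after the date of conception or LMP". The same sentence sets the later boundary from the same pair of origins: "and the beginning of the third trimester, at week 28".

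Section 8.7.1 states the cut-points again for the malformation analyses: "The second trimester will start at 14 weeks gestation and the third trimester will start at 28 weeks gestation". Its reason for stratifying is that "most structural defects have their origins in the first trimester of pregnancy during the period of organogenesis". The same section reports the other prevalence estimates overall and by trimester of exposure.

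**The concern.** Conception and the first day of the last menstrual period are different dates, about 2 weeks apart. Section 8.4 treats them as interchangeable starting points for the same week count. Because EDD or CEDD is the preferred source, and conception is the date that 8.4 derives from it, a literal reading applies the conception origin to most women. Section 8.7.1 counts in weeks of gestation, which is the LMP scale.

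Two women dosed at the same gestational age could thus fall in different trimesters because one has an EDD and the other only an LMP. Two analysts could also classify the same woman differently, depending on the section they follow. The query in 8.4 on discrepancies between LMP-derived and reported gestational age would not reveal this, since every date can be correct while the cut-point is wrong.

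The first-trimester malformation stratum has most at stake. Under the conception branch it takes in exposures that 8.7.1 calls second trimester. If early exposure does raise risk, the later exposures dilute the excess. For a registry meant to detect signals, that is the unfavourable direction.

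**Working it through.** **Inputs**
- Conception = EDD or CEDD − 38 weeks (8.4).
- Cut-points: 14 and 28 weeks after conception or LMP (8.4); 14 and 28 weeks of gestation (8.7.1).
- LMP = EDD − 40 weeks: an assumption (usual convention), not stated in the protocol.
- Reference malformation prevalence 2%, and a 4-fold increase as the size of effect sought (8.5).

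**The plan's own figure.** The boundaries are definitions, so there is no calculated value to reproduce. The 4-fold ratio used below comes from Table 1 in 8.5, which gives 3.90 for 100 live births. An exact one-sided binomial test at 5% against 2% rejects at 6 or more cases (attained level 0.0155) and reaches 80% power at a ratio of 3.896. The table entry is confirmed and not in dispute.

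**Boundaries on one scale (weeks of gestation from LMP)**

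| Rule | Second trimester starts | Third trimester starts |
|---|---|---|
| 8.4, conception branch | (40 − 38) + 14 = 16+0 | (40 − 38) + 28 = 30+0 |
| 8.4, LMP branch | 14+0 | 28+0 |
| 8.7.1 | 14+0 | 28+0 |

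There are two rules, 2 weeks apart; the LMP branch and 8.7.1 coincide. A dose at 15+0 weeks' gestation is 13 weeks after conception. It is first trimester on the conception branch and second trimester on the other two lines. If week 14 in 8.4 is read as an ordinal week, both branches move by one week and the 2-week gap between them remains.

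**Share of the first-trimester stratum affected (conception branch).** The stratum then runs from 2+0 to 15+6 weeks' gestation, which is 14 weeks. The protocol gives no distribution of exposure by week, so the share f lying at 14+0 to 15+6 has to be assumed.
- Exposure uniform: f = 2/14 = 14.3%.
- Exposure proportional to gestational age: f = (16² − 14²)/(16² − 2²) = 60/252 = 23.8%.

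At the other boundary, 2 of the 12 weeks from 28+0 to 40+0 (17%) move from the third to the second trimester.

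**Dilution, if risk is raised only for exposure before 14+0.** Apparent prevalence = (1 − f) × 8% + f × 2%; apparent ratio = that prevalence / 2%.

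| f | Apparent prevalence | Apparent ratio (true 4.0) |
|---|---|---|
| 5% | 0.95 × 8 + 0.05 × 2 = 7.7% | 3.85 |
| 14.3% | 0.857 × 8 + 0.143 × 2 = 7.1% | 3.57 |
| 23.8% | 0.762 × 8 + 0.238 × 2 = 6.6% | 3.29 |
| 50% | 0.50 × 8 + 0.50 × 2 = 5.0% | 2.50 |

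With no true excess, the ratio is 1 at every f and nothing is diluted.

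**The case against.** The strongest reply is that 8.7.1 sits in the analysis section, governs the malformation strata and is clear; an analyst who follows it misclassifies nobody. Section 8.4 also speaks of gestational weeks before it mentions conception. This stands to the extent that misclassification is a risk and not a certainty. It does not remove the contradiction, because 8.4 is the operational definition of exposure and its default branch gives different strata.

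A second reply concerns size. Section 8.7 expects most exposure after prenatal screening, so the first-trimester stratum will probably be a minority of the planned 100 to 150. Table 1 gives detectable malformation ratios of 10.10 at 20 live births and 5.38 at 50, so a shift from 4.0 to 3.6 or 3.3 would not be distinguishable there. The conception branch adds women to the stratum but loses no true first-trimester case. The teratologist or geneticist also judges the timing of exposure for each malformation (8.4). All of this is fair, and it limits the practical consequence. It does not justify leaving two rules in place.

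Three stronger readings are tempting, but the protocol does not support them.
- That the exposure window opens at LMP for women without an EDD. Section 8.4 starts the window at estimated conception for everyone. What is missing is how conception is estimated when only LMP is known.
- That 8.7.1 is a third rule. It is the same as the LMP branch.
- That the strata become non-comparable with external data. The comparators named for malformations, EUROCAT and MACDP, are described as population prevalences, and none stratified by trimester of exposure is specified.

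**Conclusion.** The definition is wrong as written. Section 8.4 applies one set of cut-points to two origins, and its default branch contradicts 8.7.1 by 2 weeks at each boundary (16+0 against 14+0, and 30+0 against 28+0), given the usual 40-week convention. Exposures at 14+0 to 15+6 and 28+0 to 29+6 weeks could be assigned to either of two trimesters.

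A reader might infer that exposures are misclassified and that the first-trimester estimate is diluted as a matter of fact. The protocol supports only the conditional statement: dilution needs the conception branch to be applied and a real first-trimester excess. The apparent ratios of about 3.6 and 3.3 are illustrations under assumed exposure patterns and an abrupt end of excess risk at 14+0. Unstratified estimates and the sample size calculation are unaffected. This cannot simply be left to the SAP, because the protocol fixes the rule in two places and an SAP that follows one may contradict the other.

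**What to change.** Use one origin in 8.4 and 8.7.1: gestational age counted from EDD or CEDD minus 280 days, or from the first day of LMP only when no EDD exists. Start the second trimester at 14+0 and the third at 28+0 weeks' gestation. If a conception scale is kept anywhere, the equivalent cut-points are 12 and 26 weeks after conception. For women dated by LMP alone, state that estimated conception, and so the start of the exposure window, is LMP plus 2 weeks. Let 8.7.1 refer to the 8.4 definition so that it is stated once.

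The cost is a short text amendment. Dose date (8.3.1) and LMP, EDD and CEDD (8.3.3) are already collected, so trimester can be derived again for anyone already enrolled, with no new data and no change to study size.
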